7.3 EFFICACY ASSESSMENT

At each study visit, the Eczema Area and Severity Index (EASI), Investigator Global Assessment (IGA), and BSA calculation will be completed and documented on the source documents and eCRF. Efficacy, via EASI, IGA, and BSA improvement should always be compared to status of condition at Visit 1 Baseline.

If possible, the same investigator who assessed the subject at Visit 1 Baseline should assess the subject at subsequent study visits. The investigator who performs the IGA and EASI should be proficient with this measure and routinely perform these evaluations.

7.3.1 Treatment of New Lesions

During the Treatment Period, new lesion(s) that appear are permitted to be treated as long as they are not in a study exclusion area; however, these lesions should not be included in the EASI, IGA, or BSA assessments. Any changes in tolerability between old lesions and new should be recorded and clearly differentiated in the source records and eCRF.

7.3.2 Photograph of Treatment Area

Photographs will be taken of the affected area(s) for informational purposes only. Camera, instructions on taking the photographs, and related items for photography will be provided by the study Sponsor. Should the subject have >4 lesions to be

photographed, the PI should choose four lesions that are representative of the overall severity of the disease and photograph these same four lesions at each study visit.

7.4 SAFETY REPORTING

7.4.1 Definitions

Adverse event - An adverse event (AE) means any untoward medical occurrence associated with the use of a drug in humans, whether or not considered drug related. An AE (also referred to as an adverse experience) can be any unfavorable and unintended sign (e.g., an abnormal laboratory finding), symptom, or disease temporally associated with the use of the drug, without judgment about causality. An adverse event can arise from any use of the drug (e.g., off-label use, use in combination with another drug) and from any route of administration, formulation, or dose, including an overdose.

Adverse reaction - An adverse reaction means any adverse event caused by a drug. Adverse reactions are a subset of all suspected adverse reactions for which there is reason to conclude that the drug caused the event.

Suspected adverse reaction - Suspected adverse reaction means any adverse event for which there is a reasonable possibility that the drug caused the adverse event. For the purposes of safety reporting, ''reasonable possibility'' means there is evidence to suggest a causal relationship between the drug and the adverse event. Suspected adverse reaction implies a lesser degree of certainty about causality than adverse reaction, which means any adverse event caused by a drug.

Suspected adverse reactions are the subset of all adverse events for which there is a reasonable possibility that the drug caused the event. Inherent in this definition (of suspected adverse reaction), and in the requirement to report them is the need for the sponsor to evaluate the available evidence and make a judgment about the likelihood that the drug actually caused the adverse event.

Unexpected Adverse Event - An adverse event or suspected adverse reaction is considered "unexpected" if it is not listed in the Investigator's Brochure

Serious - An adverse event or suspected adverse reaction is considered "serious" if, in the view of either the investigator or sponsor, it results in any of the outcomes listed in Section 7.6.

Life-threatening - An adverse event or suspected adverse reaction is considered "life-threatening" if, in the view of either the investigator or sponsor, its occurrence places the subject or subject at immediate risk of death. It does not include an

adverse event or suspected adverse reaction that, had it occurred in a more severe form, might have caused death.

If either the sponsor or investigator believes that the event meets the definition of life-threatening, it must be considered life-threatening.

7.5 ADVERSE EVENTS

Information about all AEs, whether volunteered by the subject, discovered by investigator questioning, or detected through physical examination, or other means, will be collected and recorded on the Adverse Events page of the eCRF and followed as appropriate. Adverse events will be coded using an internationally recognized dictionary.

Medical conditions/diseases present before starting study treatment are only considered adverse events if they worsen after starting study treatment (i.e., any procedures specified in the protocol). Adverse events occurring before starting study treatment, but after signing the informed consent form, are recorded on the Medical History/Current Medical Conditions page of the eCRF.

As far as possible, each AE will also be described by:

- 1. its duration (start and end dates),
- 2. the severity grade (mild, moderate, severe)
- 3. its relationship to the study product (definitely, probably, possibly, unlikely, or not related),
- 4. the action(s) taken, and,
- 5. the outcome, as relevant.

Severity of adverse events

The investigator is to classify the severity of an AE according to the following definitions:

Mild: The Subject is aware of the signs or symptoms, which are easily

tolerated.

Moderate: The signs and symptoms are sufficient to restrict, but not prevent

usual activity.

Severe: The Subject is unable to perform usual activity.

The maximum intensity of an AE (mild, moderate, or severe) will be assessed considering the possible range of intensity of the symptom(s).

Relationship of adverse event to study treatment

The investigator is to classify the relationship of the AE to the investigational product according to the definitions outlined in Table 7-6.

The following study measurements will be reported as an AE:

- 1. Any increase in the subjects' EASI score or IGA during study participation.
- 2. A negative change in Tolerability, during or immediately after study drug application.

Table 7-6: Terms for Defining Relationship of Adverse Event to Study Product

Association	Definition	
Not related	(1) the existence of a clear alternative explanation (e.g., mechanical bleeding at surgical site) or (2) non-plausibility, e.g., the subject is struck by an automobile or develops cancer a few days after product administration.	
Unlikely related	A clinical event, including laboratory test abnormality (if applicable), with an improbable time sequence to product administration and in which other drugs, chemicals for underlying disease provide plausible explanations.	
Possibly related	A clinical event, including laboratory test abnormality (if applicable), with a reasonable time sequence to administration of the drug, but which could also be explained by concurrent disease or other drugs or chemicals.	
Probably related	A clinical event, including laboratory test abnormality (if applicable), with a reasonable time sequence to administration of the drug, unlikely to be attributed to concurrent disease or other drugs or chemicals, and which follows a clinically reasonable response on withdrawal.	
Definitely related	A clinical event, including laboratory test abnormality (if applicable), with an established temporal or other association (e.g., re-challenge) and the event is not reasonably explained by the Subject's known clinical state or any other factor, based on available information.	

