3. STUDY PLAN

3.1 OVERALL STUDY DESIGN

This trial will be a double-blind, randomized, placebo-controlled, safety, tolerability and efficacy trial of SAN007 treatment regimen when administered daily for up to 28 days to subjects at least 18 years of age, with atopic dermatitis.

Subjects will enter the Screening Period once the informed consent and photographic consent process has been completed. Subjects with a total body surface area (BSA) of \geq 2% and \leq 15% atopic dermatitis involvement, in the treatable areas, and who meet all of the inclusion, and none of the exclusion criteria, will be enrolled.

Once subject eligibility is confirmed and the screening procedures completed, the subject will start the Treatment Period of the study. All enrolled subjects will receive either 5% SAN007 or placebo cream (randomized in a 2:1 ratio) OR 10% SAN007 or placebo cream (randomized in a 2:1 ratio) with the first dose applied at Visit 1 Baseline. Subjects will be instructed on how to apply the study medication twice daily, ≥8 hours between application, for 28 days. Subjects will return to the clinic on Study Days 7,14, and 28 for study-related assessments. Subjects will receive a telephone contact from the site, on Study Days 21 and 35.

Safety will be assessed by evaluating adverse events (AEs) with respect to severity, duration, and relationship to study drug.

In addition, cutaneous tolerability will be evaluated at each visit. Tolerability evaluation will be based on subjects reporting discomfort during or immediately following application of SAN007. This will also be recorded as an AE. The study exclusion areas are not to be used in this evaluation.

Efficacy will be assessed at each study visit through the completion of the IGA, EASI, and BSA calculation.

During the active treatment period, Subjects will return to the study site, according to the study schedule, for interim assessments and recording of concomitant medication(s) and adverse events (AEs).

Figure 4-1 Study Design

Screening	Baseline	+	← Treatment →			Follow-Up	
Day -7 to	Day 1	Day 7 (±2 days)	Day 14 (±2 days)	Day 21 (±2 days)	Day 28 (±2 days)	Day 35 (±2 days)	
o diw s	Visit 1	Visit 2	Visit 3	Visit 4 (Telephone Call)	Visit 5	(Telephone Call)	

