6.1.6 EASI Total Score

The final EASI score is:

EASI= C1 + C2 + C3 + C4.

An increase in EASI score, from Baseline, during study participation, will be recorded as an AE. A new adverse event will be opened only if the PI assesses an increase in severity from initial AE. Otherwise, the initial adverse event will remain open until resolution or study completion.

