6.2 INVESTIGATOR GLOBAL ASSESSMENT

The Investigator Global Assessment (IGA) should be administered by the same Investigator, or designee, for any given Subject at all study visits. Any increase in IGA grade will be recorded as an AE. It will be used to measure efficacy according to the following scale:

Grade	Score	Description			
Clear	0	No inflammatory signs of AD			
Almost Clear	1	Just perceptible erythema and just perceptible population/infiltration			
Mild	2	Mild erythema and mild population/infiltration			
Moderate	3	Moderate erythema and moderate population/infiltration			
Severe	4	Severe erythema and severe population/infiltration			

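### Protocol 6.1.6 ties an EASI adverse event to a rise from Baseline, while 7.5 names no reference visit (nor does 6.2 for IGA), so a partial rebound at or below Baseline may or may not count as an AE

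*Protocol*

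**What the plan says.** Three places in the protocol turn a change in a severity score into an AE.

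- Section 6.1.6 (EASI): "An increase in EASI score, from Baseline, during study participation, will be recorded as an AE". It adds a rule for later events: "A new adverse event will be opened only if the PI assesses an increase in severity from initial AE".
- Section 6.2 (IGA): "Any increase in IGA grade will be recorded as an AE".
- Section 7.5 (EASI and IGA), in its list of study measurements to be reported as AEs: "Any increase in the subjects' EASI score or IGA during study participation".

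Only 6.1.6 names the value against which the increase is judged. SAP 7.1 treats every reported AE as treatment-emergent, treats a missing relationship as related, and has no rule for AEs that arise from EASI or IGA rises. Protocol 8.4.5.1 bases the safety assessment mainly on AE frequency, and safety is the primary purpose of the study (Protocol 3.2, SAP 1.1.1).

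**The concern.** An increase needs a reference. Section 6.1.6 supplies one for EASI. Section 7.5 covers the same score, leaves the reference out and widens the wording to any increase, which read literally takes in a rise from the previous visit. A subject who responds and then fluctuates below the entry level is then an AE case under one section and not under the other.

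The AE tables are the primary output. The same subject can also be an efficacy responder: a fall from EASI 20 to 8 is (8 − 20)/20 = −60%, which meets the endpoint of at least 50% reduction, while the later step from 8 to 9 could put that subject in the treatment-emergent AE tables. A reader of those tables could not tell worsening relative to entry from a partial rebound.

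**Working it through.** **1. Does any other text settle the reference?**

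| Text | What it offers | Does it settle the AE rule? |
|---|---|---|
| Protocol 7.3: "Efficacy, via EASI, IGA, and BSA improvement should always be compared to status of condition at Visit 1 Baseline" | Names Visit 1 Baseline | No. It is about efficacy improvement |
| Protocol 7.5: "Medical conditions/diseases present before starting study treatment are only considered adverse events if they worsen after starting study treatment" | Requires worsening after treatment starts | No. It gives no reference level, though status before treatment fits it better than the previous visit |
| Protocol 6.1.6, rule on opening a new AE | Limits repeat events | No. It applies once a first AE exists |
| SAP 8.1, 8.2 and Table 9.0 | Change is defined against baseline; 8.1 calls a positive IGA change a worsening | Not stated for AEs, but supports Baseline |
| SAP 7.1 | Counts all reported AEs | No |

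Neither document calculates a visit-to-visit change in EASI or IGA.

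**2. One record under both readings.** Use the EASI weights in Protocol 6.1.3 (trunk 0.3, lower limbs 0.4), area score 1 in both regions and no other involvement. EASI = 0.3 × trunk intensity sum + 0.4 × lower-limb intensity sum.

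- Baseline: 0.3 × 8 + 0.4 × 6 = 4.8
- Day 7: 0.3 × 5 + 0.4 × 3 = 2.7
- Day 14: 0.3 × 6 + 0.4 × 4 = 3.4
- Day 28: 0.3 × 5 + 0.4 × 3 = 2.7

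No value exceeds 4.8, so 6.1.6 gives no AE. The step from 2.7 to 3.4 is an AE under 7.5 read literally. EASI 20, 8, 9, 7 behaves the same way. For IGA, the sequence 3, 1, 2, 1 has no grade above Baseline but one rise between visits.

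**3. Direction.** A value above Baseline cannot occur without at least one rise between successive visits. The any-rise reading therefore flags everyone whom the Baseline reading flags, plus others. Those others never exceed their Baseline value. The difference between the two flagged percentages is the share flagged by the any-rise reading only.

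**4. Scale (illustrative).** The documents give no figure to reproduce and no visit-to-visit variability. From the protocol: three post-baseline clinic assessments ("Subjects will return to the clinic on Study Days 7,14, and 28 for study-related assessments"). Assumed: independent normal noise on log EASI, and 40%, 70% and 100% of the log improvement reached at the three visits.

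| Improvement by Day 28 | Log-scale noise SD | Any value above Baseline | Any visit-to-visit rise | Any-rise only |
|---|---|---|---|---|
| 40% | 0.2 | 29% | 70% | 41% |
| 40% | 0.1 | 8% | 34% | 26% |
| 60% | 0.2 | 10% | 41% | 30% |
| 60% | 0.1 | 0.5% | 5.7% | 5% |
| none | any | 75% | 96% | 21% |

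The last row has exact values. Four exchangeable values have Baseline as their maximum with probability 1/4, so 1 − 1/4 = 75.0%. They fall in strictly decreasing order with probability 1/4! = 1/24, so 1 − 1/24 = 95.8%.

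Other assumptions move the result. With 25% to 50% improvement, noise SD 0.1 to 0.3 and 50%, 80% and 100% of the improvement at the three visits, the any-rise-only share is 23% to 48%. Continuous noise rules out ties, but EASI is built from integer sign scores and wide area bands. One integer-sign model (two regions, area score 1, latent sign noise SD 0.2, 40% improvement) flags about 4% and 15%, a gap of about 11 points.

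**The case against.** The strongest reply is that there is one rule, stated fully in 6.1.6 and abbreviated in 7.5. The list in 7.5 repeats part of 6.1.6's phrasing, the SAP measures change only from baseline, and the text in 7.5 on pre-existing conditions fits that reading. This makes Baseline the better-supported reference. It does not make 7.5 say so, and 7.5 is where a site looks to decide what to report.

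A reader might infer four stronger things that the documents do not support.

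- **That all three sections conflict.** Section 6.2 covers IGA only, so it cannot contradict the EASI rule; it just lacks a reference. Nor does 6.1.6 say that a rise from Baseline is the sole trigger. That is inferred from its wording.
- **That an improving arm collects more AEs.** In the table above it has fewer under both readings: at noise SD 0.2 the any-rise share falls from 96% with no change to 70% and then 41%. What remains is that some of its AEs would be rebounds below Baseline.
- **That sites applied different rules and so biased the comparison of strengths.** SAP 2.1 does say that some sites have only 5%/placebo and others only 10%/placebo, but nothing shows that sites followed different sections, and each randomization has its own placebo group.
- **That Baseline should become the sole AE trigger, with other rises dropped.** A subject going IGA 3, 0, 3 returns from clear to moderate on treatment without exceeding Baseline. In a safety study that should stay visible.

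It is also fair that repeat AEs are limited by 6.1.6, that new lesions are left out of EASI and IGA (Protocol 7.3.1), and that by-subject listings would let a careful reader isolate these events.

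**Conclusion.** The inconsistency stands in a limited form. For EASI, 6.1.6 and 7.5 give different triggers on their wording. For IGA, neither 6.2 nor 7.5 names a reference visit. Read literally, 7.5 can only add AE subjects, and those added never exceed Baseline. They enter the primary safety tables because SAP 7.1 counts every reported AE.

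The size is not derivable from the documents. Under independent noise of 10% to 20% and improvement of 40% to 60%, the extra subjects flagged range from about 5% to 41%, and discreteness of the scores probably lowers this. These figures show that the choice of reference can matter; they do not predict this trial's AE rate. The problem is recoverable, because EASI and IGA are recorded at Visit 1 and at every later clinic visit.

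**What to change.** Reconcile 6.1.6, 6.2 and 7.5 by stating one reference visit for EASI and IGA rises. Section 6.1.6 and the SAP's change definitions point to Visit 1 Baseline.

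The step that matters more is in the SAP. The protocol planned conduct to January 2018 and the SAP is dated 11 October 2018, so if conduct kept to plan, new protocol wording cannot change what sites recorded. Before unblinding or lock:

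1. Compare each EASI- or IGA-triggered AE with the subject's Visit 1 value.
2. Apply the stated rule uniformly in the AE tables.
3. Tabulate or list separately, by arm, the events above Baseline and those that rose from an earlier visit but stayed at or below Baseline.

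The cost is a wording correction, one data check and one extra display. No recorded AE is deleted and no new data are needed.

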7.6 SERIOUS ADVERSE EVENTS

An AE can be severe, but not necessarily serious. A serious adverse event (SAE) or suspected adverse reaction is 'serious' if, in the view of either the investigator or sponsor, results in any of the following outcomes:

- 1. death;
- 2. a life-threatening adverse event
- 3. in-subject hospitalization or prolongation of existing hospitalization;
- a persistent or significant incapacity or substantial disruption of the ability to conduct normal life functions;
- 5. a congenital anomaly or a birth defect.

Important medical events that may not result in death, be life-threatening, or require hospitalization may be considered serious when, based upon appropriate medical

San Antonio, TX

Protocol No. SAN007-02 Final Am 6: 18-Sept-2017

judgment, they may jeopardize the subject and may require medical or surgical intervention to prevent one of the outcomes listed above.

Events not considered to be serious AEs are hospitalizations for the:

- routine treatment or monitoring of the studied indication, not associated with any deterioration in condition;
- treatment, which was elective or pre-planned, for a pre-existing condition that did not worsen; and/or
- treatment on an emergency, outpatient basis for an event not fulfilling any of the definitions of serious given above and not resulting in hospital admission.

If either the sponsor or investigator believes that the event is serious, the event must be considered serious and evaluated by the sponsor.

Information about all SAEs will be collected and recorded on the Serious Adverse Event Report Form. To ensure subject safety each SAE must also be reported to the sponsor within 24 hours of learning of its occurrence and if applicable to the responsible Institutional Review Board (IRB) according to their reporting requirements.

Medical Monitor: [name]

Telephone: Office: [contact] After Hours: [contact]

[contact]

ATTENTION: [name]

(Must state: "ATTENTION:")

Email: [contact]

Sponsor: Santalis Pharmaceuticals

Pregnancy, although not itself an SAE, should also be reported on a Serious Adverse Event Report Form.

A death occurring during the study, or which comes to the attention of the investigator within four weeks after stopping treatment, must be reported.

Any serious adverse event occurring in a subject after providing informed consent, and until four weeks after stopping study drug treatment must be reported.

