Conlact	Query for status of AD since discontinuation of study

San Antonio, TX

Protocol No. SAN007-02 Final Am 6: 18-Sept-2017

	medication				
	 E.g. Has your condition been stable, improved, or worsened, since the discontinuation of study treatment? 				
Duration of Treatment and	The maximum duration of trial participation for each subject is up to 35 days:				
Trial Participation	7-day Screening Period (Day - 7)				
	28 ± 2 days Treatment (Visits 2 through 5)				
	Follow-up Call (Day 35)				
	Phone contact on Visit 4 (Day 21) and follow-up call (Day 35,) will be made with the subject.				
	If the subject's treatment is interrupted by illness or other circumstances, every attempt will be made to have the subject return to the clinic for a final visit. If the subject has remained compliant with the study medication, as determined by subject, and confirmed by product weight, if necessary, the subject will be allowed to continue the trial.				
Trial Drug, Dose and Mode of Administration	SAN007 treatment products will be provided by Santalis Pharmaceuticals, and the treatment regimen administered to the subject and explained to the LAR, if applicable.				
	The following treatment products will be provided to the subjects:				
	Cetaphil Daily Facial Cleanser- to be used on the face when washing.				
	Cetaphil Gentle Skin Cleanser- to be used on the body when showering.				
	AND STUDY DRUG LABELED WITH ONE OF THE FOLLOWING:				
	 5% SAN007 Cream - to be used morning and night, ≥ 8 hours between applications 				
	OR ION IN ION IO				
	 Placebo - to be used morning and night, ≥ 8 hours between applications 				
	OR				
	 10% SAN007 Cream - to be used morning and night, ≥ 8 hours between applications 				
	OR				
	 Placebo - to be used morning and night, ≥ 8 hours between applications 				

	The first treatment of SAN007 will be applied at the Visit 1 Baseline, then, the subject will be instructed on the procedure for self-administration at home.			
Trial Population	Up to 100 subjects, from the time of this amendment, at least 18 years of age, with a clinical diagnosis of atopic dermatitis meeting the criteria of an EASI score between 2-50 (Hanifin, 2001) with a BSA involvement of atopic dermatitis between 2%-15%, in the permitted treatment areas.			
Criteria for Evaluation	Subjects that receive one application of study medication will be included in the safety and tolerability analysis.			

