5. VISIT SCHEDULE AND ASSESSMENTS

5.1 STUDY PROCEDURES

The visit schedule and assessments are summarized in Table 5-1. A subject will have 5 visits: Screening Visit, Baseline Visit (Day 1), Treatment Visit 2 (Day 7), Treatment Visit 3 (Day 14), Telephone Call Visit 4 (Day 21) and a Final Visit 5 (Day 28) at the end of the study treatment. On Study Day 35, the subject will receive a follow-up phone call and be queried for condition status since going off study.

Confidential

San Antonio, TX Protocol No. SAN007-02 Final Am 6: 18-Sept-2017

Source documents will be completed at each subject's visit, and the data captured in the source documents will be subsequently entered into the electronic case report forms (eCRFs) by the Investigator or designee. In addition, two Telephone Visits, Visit 4 (Day 21 ± 2) and the Follow-Up (Day 35 ± 2) phone call will be conducted.

San Antonio, TX

Protocol No. SAN007-02 Final Am 6: 18-Sept.-2017

Table 5-1 Time and Events

Procedure	Screening Period Day-7 to 0	Treatment Period					Follow-Up
		Visit 1- Day 1	Visit 2- Day 7 (± 2 days)	Visit 3- Day 14 (± 2 days)	Visit 4- Day 21 (± 2 days)	Final Visit 5- Day 28 (± 2 days)	Follow-up Call- Day 35 (± 2 days)
Conduct informed consent and photography consent	x						
Record demographics	X						
Review inclusion/exclusion criteria	X	X					
Record/update all concomitant medications	x	X	х	x	X	х	
Perform a full physical examination	Х						
Record/update pertinent medical history ²	x	х	х	х	х	х	
Administer IGA and EASI	X	Х	X	X		X	
Calculate the BSA of treatment area	X	Х	Х	X		Х	
Tolerability Assessment		Х	X	X		X	
Perform an abbreviated physical examination ³		х					
If subject is female, collect urine sample and perform a β-human chorionic gonadotropin pregnancy test ⁴		х				х	
Weight study medication and record weights		х	х	x		х	
Calculate Expected Use per application		X					
Calculate Dose		X					
Calculate compliance			Х	X		X	
Dispense/re-dispense study drug ⁶		X					
Subject apply medication		X					
Instruct the subject on proper washing or the treatment area and self-application of study medication		х					
Photograph treatment area(s)		Х	Χ.	X		X	_
Instruct subject to return for next study visit		х	х		х		
Query for adverse events ⁷			X	X	Х	X	
Query for treatment regimen compliance			Х	Χ	Х	X	
Inform subject next contact will be by telephone				x		x	
Collect study medication						X	
Query for status of condition since study completion							х

Footnotes to Table 5-1: Time and Events

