- Instruct subject to return to the clinic for Visit 5 Final Visit (Day 28 \pm 2), with the study drug.

Visit 5 Final Visit (Day 28 [±2 days])

The following procedures will be performed during the Final Study Visit:

- Query for adverse events.
- Update concomitant medications including all prescription drugs, nonprescription drugs, and nutritional supplements.
- Query for treatment regimen compliance.

- Collect and weigh the study medication and record the weight.
- Calculate compliance. (i.e. Visit Day x 2 (applications per day) x EUA= expected usage) If Subject's actual compliance is ≤80% of expected compliance, re-educate and document in source.
- If subject is a female of childbearing potential, collect a urine sample and perform a β-human chorionic gonadotropin pregnancy test.
- Administer the following assessments, in which only the treatment area(s) are to be evaluated: Investigator's Global Assessment (IGA), Tolerability and BSA.
- Administer the Eczema Area Severity Index (EASI).
- Photograph the treatment area(s).
- Instruct the to return to the clinic for another study visit only if study-related adverse events persist or, in the Investigator's opinion, an additional study visit is warranted to ensure the subject's safety.

Follow-up Call (Day 35 [±2 days])

The following will be asked of the subject during the follow up telephone call:

- Query for status of AD since discontinuation of study medication
 - E.g. Has your condition been stable, improved or worsened, since discontinuing study medication?

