7.1 Adverse Events

An adverse event (AE) means any untoward medical occurrence associated with the use of a drug in humans, whether or not considered drug related. An AE (also referred to as an adverse experience) can be any unfavorable and unintended sign (e.g., an abnormal laboratory finding), symptom, or disease temporally associated with the use of the drug, without judgment about causality. An adverse event can arise from any use of the drug (e.g., off-label use, use in combination with another drug) and from any route of administration, formulation, or dose, including an overdose. Non-serious AEs will be captured through the last treatment application, Day 28/exit, and serious AEs will be captured up through 28 days following the discontinuation of therapy.

All AEs reported will be considered to be treatment-emergent. Verbatim adverse events will be mapped to PT and SOC using MedDRA 19.0.

Tabular summaries of treatment-emergent adverse events (TEAEs) in terms of number of subjects will be presented by each study arm for the following:

- PT presented in order of descending incidence in the SAN007 group then alphabetically
- SOC and PT presented in order of descending incidence in SOC, then PT, in the SAN007 group, then alphabetically by SOC and PT
 - repeat presentation for subset of study-drug related events

• SOC, PT, and maximum severity grade (mild, moderate, severe) presented alphabetically by SOC and PT

Adverse events will be counted as treatment related if they are evaluated as possibly, probably, or definitely related to study treatment. Missing relationship will be treated as related. Subjects will be counted once within each level of summarization within each study arm for the calculation of incidence.

A summary of count and percent of subjects with at least one event in the following categories will be tabulated: any TEAE, any mild TEAE, any moderate TEAE, any severe TEAE, any treatment-related TEAE, any serious TEAE, any TEAE that led to discontinuation of study drug, and any deaths. Note that any AE is only considered for its maximum severity. However a subject can have more than one AE and each may have a different maximum severity. Thus severity levels are not mutually exclusive.

A comprehensive listing of all AEs will be provided by subject, which will include the duration of each event. Duration will be calculated as the stop date of the event minus the start date, unless the event is determined ongoing at exit.

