8.0 EVALUATION OF EFFICACY PARAMETERS

Analyses in this section will be based on the FAS and the PP analysis set. The primary set for efficacy analyses will be the FAS; supportive analyses will be based on the PP. All analyses will be performed by study arm with missing data imputed using the last observation carried forward.

Throughout this section the term 'follow-up visit' will refer to any post-baseline visit, whether an office visit or a telephone contact. Only safety data and status of atopic dermatitis were to be collected at the Day 35 follow-up visit.

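### Serious events are to be captured for 28 days after treatment, but the documents disagree on whether the one routine contact in that window asks about them, and most of the window follows that contact

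*Protocol*

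**What the plan says.** **SAE window.** Protocol 7.6: "Any serious adverse event occurring in a subject after providing informed consent, and until four weeks after stopping study drug treatment must be reported". SAP 7.1: "serious AEs will be captured up through 28 days following the discontinuation of therapy". The two agree.

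**Day 35 call, protocol.** Section 5.1: "On Study Day 35, the subject will receive a follow-up phone call and be queried for condition status since going off study". Section 5.2 lists a single item, "Query for status of AD since discontinuation of study medication", with an example asking whether the condition is stable, better or worse; the synopsis repeats it. In Table 5-1 the only row marked for Day 35 is "Query for status of condition since study completion". The AE-query row is marked for Visits 2 to 5. The table extract is imperfect, but the visit lists in 5.2 confirm this.

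**Day 35 call, SAP.** Section 8.0: "Only safety data and status of atopic dermatitis were to be collected at the Day 35 follow-up visit".

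**End of AE capture.** SAP 7.1: "Non-serious AEs will be captured through the last treatment application, Day 28/exit". Footnote 7 to Table 5-1 instead has AEs collected from the first treatment for the whole trial, and foresees an AE that continues past the follow-up visit.

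**Afterwards.** No routine contact is scheduled after Day 35. Protocol 6.6 gives withdrawn subjects the last-visit procedures and does not mention the call.

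**The concern.** Safety is the stated primary purpose, and AE duration is one of its named dimensions. The plan promises four weeks of SAE capture after treatment, yet the protocol schedules no question that would elicit an SAE after Visit 5. If sites follow the protocol, late SAEs reach the database only when a subject or another party raises them. A report repeating the SAP's sentence on 28-day capture would then let the reader take no late events recorded as no late events occurred.

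A second consequence concerns which events count. The documents give different answers on when AE capture closes, so two programmers could treat the same post-treatment event differently. An AE still open at Visit 5 may also never receive a stop date, because the one later scheduled contact does not ask about it.

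**Working it through.** **1. Window length.** Four weeks = 4 × 7 = 28 days, so protocol 7.6 and SAP 7.1 match. Call this W = 28.

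**2. Inputs.** Visit 5 is Day 28 ± 2 and the call is Day 35 ± 2 (protocol 5.2, Table 5-1). Assume the last application falls on the day of Visit 5, so the stop day S is 26 to 30 and the call day C is 33 to 37.

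**3. Protocol reading.** The call has no AE question, so 0 of 28 days are actively queried.

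**4. SAP reading.** If the call does collect safety data, days covered = C − S, and days after the last scheduled contact = W − (C − S).

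| Case | S | C | Covered | Not covered | Share not covered |
|---|---|---|---|---|---|
| Nominal | 28 | 35 | 7 | 21 | 21/28 = 75% |
| Late stop, early call | 30 | 33 | 3 | 25 | 25/28 = 89% |
| Early stop, late call | 26 | 37 | 11 | 17 | 17/28 = 61% |

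**5. Early withdrawal.** For a subject who stops on Day 10, the window ends on Day 10 + 28 = Day 38. A Day 35 call would fall 35 − 10 = 25 days into it and leave 3 days. Without the call, nothing after the withdrawal visit is routinely queried. The documents do not say which applies.

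**6. A non-serious event starting on Day 32, read against each passage.**

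| Passage | Result |
|---|---|
| Table 5-1, footnote 7 | Within the collection period, if the call counts as part of the trial |
| Protocol 5.2 and Table 5-1 | No question that would elicit it |
| Protocol 7.5 | Recorded if the subject volunteers it |
| SAP 7.1 | Outside the capture period |
| SAP 8.0 | Obtainable at Day 35 |
| SAP Table 9.0 | Treatment-emergent, since the rule has a start and no end |

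These cannot all be applied together.

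**7. Duration.** SAP 7.1 takes stop date minus start date unless the event is ongoing at exit. The protocol's call does not ask whether an event open at Visit 5 has resolved. If the subject answers that the eczema is worse, protocol 7.5 treats worsening of a pre-existing condition as an AE, but SAP 8.4 only lists the answer, and no rule connects the two.

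**8. Participation figure (minor, separate).** The synopsis states "The maximum duration of trial participation for each subject is up to 35 days". Screening plus treatment reproduces it: 7 + 28 = 35. Including the follow-up call, which the same entry lists, gives 7 + 35 = 42, or 7 + 37 = 44 with the window.

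**The case against.** The best defence is that protocol 7.6 is a reporting duty, not a visit schedule. Its rule on deaths is openly passive: it covers deaths that the investigator comes to know of. A four-week duty without a four-week call is not a contradiction. That stands, and it is why an extra call is optional. It does not explain why SAP 8.0 describes safety collection at Day 35 that no protocol procedure provides.

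Several stronger readings are tempting, and the documents do not support them.

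- *Nothing follows the call.* Only routine contact ends. Footnote 7 and the Visit 5 list allow a return visit for a persisting AE or at the investigator's discretion, protocol 6.5 follows subjects discontinued for an AE, and known SAEs must still be reported.
- *Persisting reactions are lost.* AEs are queried at Visit 5, and persistence can trigger a return. The question on worsening could also bring out a skin reaction in a treated area.
- *Post-treatment safety is unobserved.* The accurate description is not actively solicited.
- *The patch-test range in protocol 1.1 (less than 0.1% to 6.6%) sizes the missed events.* Those are diagnostic results in people with contact dermatitis, eczema, photosensitivity disorders or suspected allergy. This trial excludes known sensitivity (protocol 4.3), and the documents give no rate of first onset after the last dose.
- *The main safety tables are compromised.* AEs are queried on Days 7, 14, 21 and 28, and the SAP plans no separate post-treatment safety table.

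**Conclusion.** The point holds as a conflict between protocol and SAP over what Day 35 collects and when AE capture ends, together with an SAE window that is mostly passive. Active questioning covers 0 of 28 post-treatment days on the protocol's wording. On the SAP's wording, about 21 of 28 days (17 to 25, or 61% to 89%) follow the last scheduled contact. These figures assume a completer whose last application coincides with Visit 5. They measure days of questioning, not events; the documents give no SAE rate from which to estimate a number missed.

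The contact schedule is the same in every arm, so nothing here points to bias between arms. What is limited is the completeness of late SAE counts and what may be claimed from them. The conflict should be settled before the safety results are reported, because it decides which events are counted and how a zero is read.

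**What to change.** 1. Add an AE/SAE question to the existing Day 35 call, including whether AEs open at Visit 5 have resolved and when. Change the synopsis, protocol 5.2 and Table 5-1 together.
2. State that withdrawn subjects also receive the call.
3. Align the AE cut-off in SAP 7.1 with SAP 8.0, so that one date governs non-serious AEs.
4. State in SAP 7.1 that SAEs after the call are spontaneous reports only. A further call four weeks after the last application would close the gap but is optional.
5. Correct the 35-day participation figure as a separate, minor edit.

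The planned study dates end in January 2018 and the SAP is dated October 2018, so conduct may already be over. In that case, amend SAP 7.1 and 8.0 to say what was actually asked at Day 35, and do not report the 28-day window as actively captured.

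The cost is a few questions on a call already scheduled plus wording changes, or wording alone if conduct has ended. AE counts may rise slightly.
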